9.5 Evaluation of post-use structural and functional integrity of the e-Device

Following the subject's final self-administration using the e-Device, the e-Device will be visually inspected for structural integrity and damage (ie, clear evidence of damage/compromised structural integrity—not superficial, cosmetic imperfections). The e-Device will also be evaluated for functional integrity (ie, proper functioning) using a training cassette as specified in the in vitro e-Device functional testing directions. All evaluations will be performed by appropriately trained site staff.

9.6 Evaluation of safe and effective self-injection

Safe and effective self-injection will be evaluated by the HCP. Subject self-injection of the complete dose of CZP will be confirmed by a visual inspection of the CZP-cassette(s) which shows the PFS container to be empty. During self-injection, if the skin sensor at the injection port loses contact with the skin, the e-Device will withdraw the needle and stop administration of CZP. If less than five minutes have elapsed since loss of contact with skin, the subject can reposition the e-Device on a new clean injection site and resume and complete the self-injection. If the subject is unable to complete the self-injection and deliver the entire dose of medication (ie, the device indicates incomplete administration and the CZP-cassette is not seen to be empty), the HCP evaluating the self-injection will document the incomplete self-injection, note the reason why the complete dose was not administered, and using his/her best medical judgment, advise the subject regarding any further dosing. The self-injection will be considered safe if there are no AEs related to use of the e-Device (ADEs) that would preclude continued use of the e-Device for self-injection.

For subjects on the Q4W dosing regimen who will self-inject twice (2×200mg CZP) at each visit, each injection will be evaluated for safety and effectiveness using the above criteria. The primary endpoint of safe and effective self-injection for subjects on the Q4W dosing regimen will be met only if both self-injections are determined to be safe and effective.

10 ASSESSMENT OF SAFETY

In this study, safety reporting requirements apply to the IMP and to all constituents of the investigational device (including the e-Device auto-injector, and the CZP-cassette) per 21 CFR 312.32, 21 CFR 812.150, and 21 CFR 812.3. Subjects in the study are experienced at self-injection and will be aware of their usual injection experience and events typically seen during the normal course of an injection. Effects that are considered usual by the subject and the HCP (eg, minor pain, bruising, or bleeding) during the course of self-injection are not to be classified as AEs.

10.1 Adverse events (IMP)

10.1.1 Definitions (IMP)

10.1.1.1 Adverse event (IMP)

An adverse event (AE) is any untoward medical occurrence in a patient or clinical investigation subject administered a pharmaceutical product that does not necessarily have a causal relationship with this treatment. An AE can therefore be any unfavorable and unintended sign (including an abnormal laboratory finding), symptom, or disease temporally associated with the use of a medicinal (investigational) product, whether or not related to the medicinal (investigational) product.

In order to ensure complete safety data collection, all AEs occurring during the study (ie, after the signing of the Informed Consent form), including any pretreatment and posttreatment periods required by the protocol, must be reported in the eCRF even if no IMP was taken but specific study procedures were conducted. This includes all AEs not present prior to the initial visit and all AEs that recurred or worsened after the initial visit.

Signs or symptoms of the condition/disease for which the IMP is being studied should be recorded as AEs only if their nature changes considerably or their frequency or intensity increases in a clinically significant manner as compared to the clinical profile known to the Investigator from the subject's history or the Baseline Period.

10.1.1.2 Serious adverse event (IMP)

Once it is determined that a subject experienced an AE, the seriousness of the AE must be determined. An SAE must meet 1 or more of the following criteria:

- Death
- Life-threatening
(Life-threatening does not include a reaction that might have caused death had it occurred in a more severe form.)
- Significant or persistent disability/incapacity

- Congenital anomaly/birth defect (including that occurring in a fetus)
- Important medical event that, based upon appropriate medical judgment, may jeopardize the patient or subject and may require medical or surgical intervention to prevent 1 of the other outcomes listed in the definition of serious

(Important medical events may include, but are not limited to potential Hy's Law [see Section 10.1.1.3], allergic bronchospasm requiring intensive treatment in an emergency room or at home, blood dyscrasias that do not result in inpatient hospitalization, or the development of drug dependency or drug abuse.)

- Initial inpatient hospitalization or prolongation of hospitalization

(A patient admitted to a hospital, even if he/she is released on the same day, meets the criteria for the initial inpatient hospitalization. An emergency room visit that results in admission to the hospital would also qualify for the initial inpatient hospitalization criteria. However, emergency room visits that do not result in admission to the hospital would not qualify for this criteria and, instead, should be evaluated for 1 of the other criteria in the definition of serious [eg, life-threatening adverse experience, important medical event].

Hospitalizations for reasons not associated with the occurrence of an AE [eg, preplanned surgery or elective surgery for a pre-existing condition that has not worsened or manifested in an unusual or uncharacteristic manner] do not qualify for reporting. For example, if a subject has a condition recorded on his/her medical history and later has a preplanned surgery for this condition, it is not appropriate to record the surgery or hospitalization as an SAE, since there is no AE upon which to assess the serious criteria. Please note that, if the pre-existing condition has worsened or manifested in an unusual or uncharacteristic manner, this would then qualify as an AE and, if necessary, the seriousness of the event would need to be determined.)

10.1.1.2.1 Anticipated serious adverse events (IMP)

The following Anticipated SAEs are anticipated to occur in the population studied in this protocol at some frequency that is independent of drug exposure.

This list does not change the Investigator's obligation to report all SAEs (including Anticipated SAEs) as detailed in Section 10.1.1.2.

Table 10–1: Anticipated serious adverse events for study population

Population	Anticipated SAE
Rheumatoid arthritis	Rheumatoid arthritis
Crohn's disease	Crohn's disease Perianal abscess Abdominal pain
Psoriatic arthritis	Psoriatic arthritis
Ankylosing spondylitis	Ankylosing spondylitis

SAE=serious adverse event

10.1.1.3 Adverse events of special interest (IMP)

An AE of special interest is any AE that a regulatory authority has mandated be reported on an expedited basis, regardless of the seriousness, expectedness, or relatedness of the AE to the administration of a UCB product/compound. For the present study, the AEs of special interest are as follows:

- Serious infections, including opportunistic infections
- Malignancies, including lymphoma
- Congestive heart failure
- Demyelinating-like disorders
- Aplastic anemia, pancytopenia, thrombocytopenia, neutropenia, and leucopenia
- Serious bleeding events
- Lupus and lupus-like syndrome
- Serious skin reactions (ie, Stevens Johnson Syndrome, toxic epidermal necrosis, and erythema multiforme)

Potential Hy's Law, defined as $\geq 3x$ upper limit of normal (ULN) alanine aminotransferase (ALT) or aspartate aminotransferase (AST) with coexisting $\geq 2x$ ULN total bilirubin in the absence of $\geq 2x$ ULN alkaline phosphatase (ALP), with no alternative explanation for the biochemical abnormality, must ALWAYS be reported to UCB as an AE of special interest (ie, without waiting for any additional etiologic investigations to have been concluded). Follow-up information should then be reported if an alternative etiology is identified during investigation and monitoring of the subject.

10.1.2 Procedures for reporting and recording adverse events (IMP)

The subject will be given the opportunity to report AEs spontaneously. A general prompt will also be given at each study visit to detect AEs. For example:

“Did you notice anything unusual about your health (since your last visit)?”

In addition, the Investigator should review any self-assessment procedures employed in the study.

10.1.2.1 Description of adverse events (IMP)

When recording an AE, the Investigator should use the overall diagnosis or syndrome using standard medical terminology, rather than recording individual symptoms or signs. The eCRF and source documents should be consistent. Any discrepancies between the subject's own words on his/her own records (eg, diary card) and the corresponding medical terminology should be clarified in the source documentation.

Details for completion of the Adverse Event eCRF (including judgment of relationship to IMP) are described in the eCRF Completion Guidelines.

10.1.2.2 Rule for repetition of an adverse event (IMP)

An increase in the intensity of an AE should lead to the repetition of the AE being reported with:

- The outcome date of the first AE that is not related to the natural course of the disease being the same as the start date of the repeated AE, and the outcome of “worsening”
- The AE verbatim term being the same for the first and repeated AE, so that the repeated AE can be easily identified as the worsening of the first one

10.1.2.3 Additional procedures for reporting serious adverse events (IMP)

If an SAE is reported, UCB must be informed within 24 hours of receipt of this information by the site (see contact information for SAE reporting listed in the Serious Adverse Event Reporting section at the front of the protocol). The Investigator must forward to UCB (or its representative) a duly completed “Investigator SAE Report Form for Development Drug” (SAE report form) provided by UCB, even if the data are incomplete, or if it is obvious that more data will be needed in order to draw any conclusions. Information recorded on this form will be entered into the global safety database.

An Investigator SAE report form will be provided to the Investigator. The Investigator SAE Report form must be completed in English.

It is important for the Investigator, when completing the SAE report form, to include the assessment as to a causal relationship between the SAE and the IMP administration. This insight from the Investigator is very important for UCB to consider in assessing the safety of the IMP and in determining whether the SAE requires reporting to the regulatory authorities in an expedited manner.

Additional information (eg, autopsy or laboratory reports) received by the Investigator must be provided within 24 hours. All documents in the local language must be accompanied by a translation in English, or the relevant information included in the same document must be summarized in the Investigator SAE report form.

The Investigator is specifically requested to collect and report to UCB (or its representative) any SAEs (even if the Investigator is certain that they are in no way associated with the IMP), up to completion of the follow-up visit for each subject, and to also inform participating subjects of the need to inform the Investigator of any SAE within this period. Serious AEs that the Investigator

thinks may be associated with the IMP must be reported to UCB regardless of the time between the event and the end of the study.

Upon receipt of the SAE report form, UCB will perform an assessment of expectedness of the reported SAE. The assessment of the expectedness of the SAE is based on the Investigator's Brochure.

10.1.3 Follow up of adverse events (IMP)

An AE should be followed until it has resolved, has a stable sequelae, the Investigator determines that it is no longer clinically significant, or the subject is lost to follow up. This follow-up requirement applies to AEs, SAEs, and AEs of special interest.

If an AE is ongoing at the end of the study for a subject, follow up should be provided until resolution/stable level of sequelae is achieved, or until the Investigator no longer deems that it is clinically significant, or until the subject is lost to follow up. If no follow up is provided, the Investigator must provide a justification.

Information on SAEs obtained after clinical database lock will be captured through the Patient Safety (PS) database without limitation of time.

10.2 Adverse events (investigational device)

10.2.1 Definitions (investigational device)

10.2.1.1 Adverse Events (investigational device)

An AE for an investigational device is any untoward medical occurrence, unintended disease or injury, or untoward clinical sign (including abnormal laboratory findings) in subjects enrolled in the study, including any pre- and posttreatment periods (as required by the protocol). This includes the following:

- Events considered unrelated or related to the investigational medical device
- Events related to the procedures involved (even if no investigational device was used).

For users or other persons (eg, caregivers), AEs for a device are restricted to only events related to the investigational medical device.

In order to ensure complete safety data collection, all AEs occurring during the study (ie, after the signing of the Informed Consent form), including any pretreatment and posttreatment periods required by the protocol, must be reported in the eCRF even if no investigational device was used but specific study procedures were conducted. This includes all AEs not present prior to the initial visit and all AEs that recurred or worsened after the initial visit.

Signs or symptoms of the condition/disease for which the Investigational Device is being studied should be recorded as AEs only if their nature changes considerably or their frequency or intensity increases in a clinically significant manner as compared to the clinical profile known to the Investigator from the subject's history or the Baseline Period.

10.2.1.2 Serious adverse event (investigational device)

Once it is determined that a subject experienced an AE for an investigational device, the seriousness of the AE must be determined. An SAE must meet 1 or more of the following criteria:

- Death
- Serious deterioration in the health of the subject that results in at least 1 of the following:
 - Life-threatening illness or injury
 - Permanent impairment of a body structure or body function
 - Inpatient or prolonged hospitalization
 - Medical or surgical intervention to prevent life-threatening illness or injury or permanent impairment to a body structure or body function
 - Fetal distress, fetal death, or a congenital abnormality or birth defect

Planned hospitalization for a pre-existing condition, or a procedure required by the protocol, without serious deterioration in health, is not considered a serious adverse event.

10.2.1.3 Device- or procedure-related

10.2.1.3.1 Adverse device effect (investigational device)

An adverse device effect (ADE) is an AE related to the use of an investigational device. An ADE must meet 1 or more of the following criteria:

- Adverse event resulting from insufficiencies or inadequacies in the instructions for use, the deployment, the implantation, the installation, the operation, or any malfunction of the investigational medical device.
- Adverse event that is a result of a use error or intentional misuse.

10.2.1.3.1.1 Unanticipated adverse device effect (investigational device)

An unanticipated adverse device effect (UADE) is any ADE that meets 1 or more of the following criteria:

- Serious adverse effect on health or safety or any life-threatening problem or death caused by, or associated with a device, if that effect, problem, or death was not previously identified in nature, severity, or degree of incidence in the application
- Any other unanticipated serious problem associated with a device that relates to the rights, safety, or welfare of subjects.

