4 STUDY VARIABLES

4.1 Study outcome variables

4.1.1 Primary outcome variable

The primary outcome variable is the proportion (%) of subjects able to self-administer safe and effective injections using the e-Device at Visit 2. Safe and effective self-injection will be evaluated by the HCP and is defined as:

- Complete Dose Delivery: Subject self-injected the complete dose of CZP as confirmed by a visual inspection of the CZP-cassette(s) which shows the PFS container to be empty and

- No AEs related to use of the e-Device (ADEs) that would preclude continued use of the e-Device for self-injection

During self-injection, if the skin sensor at the injection port loses contact with the skin, the e-Device will withdraw the needle and stop administration of CZP. If less than five minutes have elapsed since loss of contact with skin, the subject can reposition the e-Device on a new clean injection site and resume and complete the self-injection. If the subject is unable to complete the self-injection and deliver the entire dose of medication (ie, the device indicates incomplete administration and the CZP-cassette is not seen to be empty), the HCP evaluating the self-injection will document the incomplete self-injection, note the reason why the complete dose was not administered, and using his/her best medical judgment, advise the subject regarding any further dosing.

For subjects on the Q4W dosing regimen who will self-inject twice (2×200mg CZP) at each visit, each injection will be evaluated for safety and effectiveness using the above criteria. The primary endpoint of safe and effective self-injection for subjects on the Q4W dosing regimen will be met only if both self-injections are determined to be safe and effective.

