10.2.2.1 Adverse events

Details for completion of the Adverse Event eCRF (including judgment of relationship to Investigational Device or Study procedure) are described in the eCRF Completion Guidelines.

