8.1.1 Derivations of primary outcome variable

The primary endpoint of safe and effective self-injection will be met if both criteria are confirmed by the HCP and are recorded on the Study Medication Administration CRF form: (1) subject self-inject the complete dose of CZP as confirmed by visual inspection of the CZP-cassette(s) which shows the PFS container to be empty; (2) there are no AEs related to use of the e-Device (ADEs) that would preclude continued use of the e-Device for self-injection.

No imputation of missing data will be performed.

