10.2.2 Adverse device effect (investigation device)

An adverse device effect (ADE) is an AE related to the use of an investigational device.

The incidence of ADEs and serious ADEs will be summarized separately by MedDRA SOC, high level term, and PT. Each ADE will be listed for the SS.

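### Protocol 10.2.1.3.1 gives two incompatible definitions of an adverse device effect, the term that labels the safety half of the primary endpoint

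*Protocol*

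**What the plan says.** Protocol 10.2.1.3.1 opens by defining an ADE as an AE related to use of an investigational device. The next sentence reads "An ADE must meet 1 or more of the following criteria". Two criteria follow:

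- "Adverse event resulting from insufficiencies or inadequacies in the instructions for use, the deployment, the implantation, the installation, the operation, or any malfunction" of the device
- "Adverse event that is a result of a use error or intentional misuse"

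The safety half of the primary endpoint in Protocol 4.1.1 is "No AEs related to use of the e-Device (ADEs) that would preclude continued use of the e-Device for self-injection". The same wording, or near it, appears in Protocol sections 1, 9.6 and 12.3.1 and in SAP 8.1. Protocol 4.1.2 and SAP 8.2.1 use it for the Visit 1 secondary endpoint. None of these places cites 10.2.1.3.1.

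SAP 10.2.2 carries only the broad sentence: "An adverse device effect (ADE) is an AE related to the use of an investigational device". On derivation, SAP 8.1.1 says "The primary endpoint of safe and effective self-injection will be met if both criteria are confirmed by the HCP", as recorded on the Study Medication Administration form. SAP 3.9 lists no change to protocol-defined analyses.

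**The concern.** Suppose a trained subject follows the instructions, the device works as designed, and the automatic needle insertion still causes an unusual haematoma. (The example is hypothetical.) The event is related to device use, so it is an ADE under the opening sentence. On a plain reading it involves no inadequacy, malfunction, use error or misuse, so it is not an ADE under the next sentence.

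Several things hang on the answer:

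- the safety half of the primary endpoint and of the Visit 1 endpoint;
- the ADE and SADE tables in SAP 10.2.2;
- the 24-hour ADE report in Protocol 10.2.3.1.1;
- the SADE and UADE classes, which the Protocol defines as kinds of ADE and which therefore inherit any restriction.

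The study asks whether trained users can inject safely with this device. Harm from the device working as intended is central to that question.

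**Working it through.** The plan has no figure to reproduce here: Protocol 12.8 says the study is not powered for any endpoint. The check is mainly a comparison of texts.

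**1. Where each wording appears**

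| Place | Test for an ADE, or for safe |
|---|---|
| Protocol 10.2.1.3.1, first sentence | Related to device use |
| Protocol 10.2.1.3.1, second sentence | Must arise from inadequacy, malfunction, use error or misuse |
| Protocol 4.1.1, 9.6, 12.3.1 | Related to e-Device use, and would preclude further use |
| SAP 8.1, 8.1.1 | As Protocol 4.1.1, confirmed by the HCP |
| SAP 10.2.2 | Related to device use |
| Protocol 10.2.2.1 (AE form) | Judgment of relationship to device or procedure |

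The restriction appears once, in the only place where the Protocol defines the term in full.

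**2. Is the second sentence a condition or a list of examples?** The Protocol uses the same formula for SAEs in 10.1.1.2 and 10.2.1.2, where it is plainly a required condition. Where the list is open, the Protocol says that the term includes the items (10.2.1.1 for device AEs, 10.2.1.3.3 for device deficiencies). By the document's own usage, the two ADE criteria are compulsory.

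**3. Direction of error.** Events meeting the narrow wording are a subset of those meeting the broad wording. Applying the narrow one can remove events from the ADE class and never add any, so any resulting error in the proportion is towards safe.

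**4. Scope for inconsistency.** Protocol 5.1.2 plans about 45 sites for at least 60 treated subjects, or 60/45 ≈ 1.3 per site at the minimum. Many HCPs would each judge one or two people, with little chance to settle on a common reading.

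**5. Size, for illustration.** Inputs are the exact binomial 90% interval (Protocol 12.2) and the Visit 1 numbers in Protocol 12.8: 60 overall, at least 15 per dosing group and at least 10 with impaired hand function. The lower bound L for x successes in n solves

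sum over k = x to n of C(n,k) L^k (1−L)^(n−k) = 0.05

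- No failure (x = n): L = 0.05^(1/n). For n = 15, 0.05^(1/15) = 0.819.
- One failure (x = n−1): n L^(n−1) (1−L) + L^n = 0.05. For n = 15, L = 0.721.

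| n | No failure: estimate, lower bound | One failure: estimate, lower bound | Drop in lower bound |
|---|---|---|---|
| 60 | 100%, 95.1% | 98.3%, 92.3% | 2.8 points |
| 15 | 100%, 81.9% | 93.3%, 72.1% | 9.8 points |
| 10 | 100%, 74.1% | 90.0%, 60.6% | 13.5 points |

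These are Visit 1 minimum numbers. SAP 8.1.2 uses as denominator the subjects who self-injected at Visit 2, which may be fewer.

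**The case against.** A reader might infer that harm from a correctly used, working device is not an ADE and cannot fail the safety half of the endpoint. The documents do not support that.

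- The sentence just before the restriction defines an ADE by relatedness alone. The section contradicts itself; it does not clearly restrict.
- Protocol 9.6 says "The self-injection will be considered safe if there are no AEs related to use of the e-Device (ADEs) that would preclude" continued use, and does not mention the two criteria. An HCP following that text can fail the injection, and under SAP 8.1.1 the HCP's record decides the endpoint.
- The first criterion lists inadequacy of deployment or operation separately from malfunction. Some harm without a malfunction could be argued to fit, so the excluded class may be small.

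A reader might also infer that sites will collect ADEs on a different definition from the one analysed. That is not shown. Protocol 10.2.2.1 sends the AE form, "including judgment of relationship to Investigational Device or Study procedure", to the eCRF Completion Guidelines, which are not part of the documents.

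Nor would the event disappear. All AEs are recorded whether related or not (Protocol 10.2.1.1), relationship to the device is listed for each (SAP 10.2.1), and SAEs go to the sponsor within 24 hours whatever the cause (Protocol 10.1.2.3). Finally, the interval figures show what any single failure does; they are not specific to this defect.

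All of this stands. It limits the consequence but does not remove the contradiction. The endpoint text puts the ADE label on its safety criterion, and someone who looks up that label in the Protocol finds the compulsory criteria. The SAP cannot correct a judgment already made at the site. The rule in Protocol section 10 that usual injection effects are not AEs is a separate matter and does not settle how unusual harm is classed.

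**Conclusion.** The Protocol's ADE definition is wrong as written, because two consecutive sentences cannot both hold for harm from a correctly used, normally working device. The endpoint text and the SAP favour the broad sentence, but the Protocol never says that it prevails. HCPs could therefore classify the same event differently, and a departure towards the narrow rule can only raise the reported success proportion.

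The table above assumes exactly one endpoint-failing event with no inadequacy, malfunction, use error or misuse. The documents give no rate for such events. They also set no hypothesis test and no success threshold, so no pass or fail conclusion changes, and bias is a possibility rather than a demonstrated result. The point deserves correction before events are classified, but it ranks below a defect that must be fixed for the study to be interpretable.

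**What to change.** In Protocol 10.2.1.3.1, replace "An ADE must meet 1 or more of the following criteria" with *This includes, but is not limited to*, so that relatedness to use of the e-Device or CZP-cassette is the test and the two criteria become examples. State the same definition in SAP 8.1.1 and 10.2.2, and in the instructions for the Study Medication Administration form on which the HCP records the safety criterion.

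The cost is one sentence in a protocol amendment, matching text in the SAP, and a note to sites. A few more AEs may be classed as ADEs and sent on the 24-hour form, and the success proportion may come out slightly lower. Nothing else in the design changes.
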